Implant Surgery					X								
LABORATORY													
Serum chemistry , hematology, urinalysis			X ³						X		X		X
Urine Pregnancy ⁶			X ³						X		X		X
HIV testing			X ³										
Genetic testing through eyeGENE			X ⁷										
Serum for antibody/CNTF concentration			X						X		X	X	X

¹ Baseline 1 Screening will occur within 7 weeks of implant surgery; Baseline 2 Screening will occur within 4 weeks of Baseline 1.

² Baseline 3 will occur < 4 days prior to implant surgery

³ ECG and pre-op laboratory testing should be performed within the timeframe mandated by the OR.

⁴ Measurement or exams should be taken at any point within 7 weeks preceding implant surgery.

⁵ Measurement at Baseline 1 must establish a minimum of 7 ROI's; measurement at Baseline 2 must verify a minimum of 7 of the previously established ROI's for measurement throughout the study period.

⁶ Urine pregnancy test will only be performed on premenopausal women.

⁷ Genetic testing will be offered to patients with diseases for which eyeGENE offers testing. Separate consent is required and patients can refuse to submit blood for genetic testing but still participate in the present study.

Photoreceptor Structure in a Phase 2 Study of Encapsulated Human NTC-201 Cell Implants Releasing Ciliary Neurotrophic Factor (CNTF) for Participants with Retinitis Pigmentosa Using Rates of Change in Cone Spacing and Density as the Primary Outcome

1 Background and Rationale

Retinitis Pigmentosa (RP) is a group of hereditary disorders whose common feature is a progressive deterioration of the rod and cone photoreceptors in the retina, which results in the reduction and loss of both peripheral and central vision. Histopathologic studies in naturally occurring and genetically engineered animal models of photoreceptor dysfunction and death in the condition termed retinitis pigmentosa (RP) have indicated the promise of ciliary neurotrophic factor (CNTF) as an effective therapeutic agent for reducing photoreceptor loss associated with degeneration of the cells of the outer retina. CNTF is one of several neurotrophic factors that are produced endogenously by neurons or supporting glial cells and has been demonstrated to be highly effective in retarding photoreceptor neuron loss in 12 animal RP models with various forms of retinal degeneration.

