4.2 Inclusion Criteria

1. Participant must be between 18 and 55 years of age.
2. Participant must have a diagnosis of retinitis pigmentosa or Usher syndrome type 2 or 3.
3. Participant must understand and sign the protocol informed consent. If the participant's vision is impaired to the point where he/she cannot read the informed consent document, the document will be read to the participant in its entirety.
4. Best-corrected visual acuity must be no worse than 20/63 (at least 59 letters).
5. Participants must have clear natural lenses.
6. Participants must have less than 6 diopters myopia.
7. Participants must be medically able to undergo ophthalmic surgery for the NT-501 device insertion and be able to undergo all assessments and tests associated with the protocol.

8. Females of childbearing potential (**women with last menses \leq 1 year prior to screening**) must agree to use an effective form of birth control from study onset until they complete the study.
9. Participants must have reproducible baseline AOSLO image montages at 2 baseline imaging sessions with quality suitable to identify a minimum of 7 regions of interest (ROIs) at which reliable cone spacing and/or density measures can be made over the central 5.7 degrees.
10. Participants must have interocular symmetry of disease severity as measured by cone spacing, with a difference of less than 2 standard deviations in average cone spacing z-scores at the selected ROIs between the 2 eyes.
11. Participant's clinical diagnosis must be consistent with retinal degeneration in the set of retinitis pigmentosa (RP) dystrophies characterized by the following features:
 - a) clinical evidence of progressive photoreceptor cell dysfunction and degeneration of the outer retina
 - b) intraretinal 'bone-spicule'-like pigment observed on clinical examination
 - c) peripheral visual field constriction documented on standard testing
 - d) symptomatic night blindness
 - e) reduction of both rod and cone electroretinogram (ERG) responses.

For purposes of this study, individuals diagnosed with Retinitis Pigmentosa or Usher Syndrome Type 2 or Type 3 (without profound deafness or cochlear implants) who meet the inclusion criteria will be considered as potential candidates for this study. A maximum of 4 Usher Syndrome Type 2 or Type 3 participants may be enrolled in this trial.

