4.3 Exclusion Criteria

1. Participant is medically unable to comply with study procedures or follow-up visits.
2. Participant who has any of the following lens opacities: cortical opacity $>$ standard 3, posterior subcapsular opacity $>$ standard 3, or a nuclear opacity $>$ standard 3 as measured on the AREDS clinical lens grading system; or participant is pseudophakic or aphakic.
3. Participant has history of corneal opacification or lack of optical clarity.

4. Participant has undergone LASIK surgery or other refractive surgery for either eye.
5. Participant has nystagmus.
6. Participant has greater than 6 diopters myopia.
7. Participant has cystoid macular edema with cysts present within 4 degrees of the foveal center.
8. Participant has fewer than 7 ROIs present on 2 baseline AOSLO image montages.
9. Participant has retinal vascular disease such as diabetic retinopathy or prior retinal vascular occlusive disease.
10. Participant has chronic requirement (e.g., \geq 4 weeks at a time) for ocular medications or has disease(s) that in the judgment of the examining physician are vision threatening, toxic to the lens, retina, or optic nerve or may affect the primary outcome.
11. Participant has a requirement of acyclovir and/or related products during study duration. To be eligible for this study, the participant must discontinue use of these products prior to enrollment and must not continue with the products until after they have completed the study.
12. Participant is receiving systemic steroids or other immunosuppressive medications.
13. Participant is currently participating in or has participated in any other clinical trial of a drug by ocular or systemic administration within the last 6 months.
14. Participant has previous exposure to an intra-ocular device or implant into the eye (excluding intra-ocular lens).
15. Participant has uveitis or other retinal inflammatory disease.
16. Participant has a history of myocardial infarction within the last 12 months.
17. Participant is pregnant or lactating.
18. Participant is considered immunodeficient or has a known history of HIV. A laboratory test for HIV will be performed, and a positive result is also an exclusion criterion.
19. Participant with a history of ocular herpes zoster.
20. Participant is on chemotherapy.

21. Participant has a history of malignancy, except study participant with cancer treated successfully ≥ 5 years prior to inclusion in the trial.

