- Whole blood collected for genetic testing through the eyeGENE research consortium, as applicable, for patients with autosomal dominant RP and other retinal degenerations that are included on the list of conditions tested by eyeGENE.

For consideration of eligibility, study participants will be screened to ensure eligibility. Some screening evaluations will not be completed on the initial screening day, however all screening evaluations, which are completed within 1 month of the initial screening visit, can be used to establish eligibility.

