4.8 Enrollment, Randomization, Masking and Unmasking

Enrollment and Randomization:

To determine eligibility, prospective participants will be screened per the screening examination cited in Section 4 and Table 1 at the time of their routine visit for RP evaluation.

Participants will be enrolled and randomized in two stages. In the first stage, if the participant appears to be a likely candidate (based upon the patient's known medical history), the PI or a delegate will obtain the participant's informed consent. After receiving the participant's consent, the clinic will complete screening assessments during the Baseline 1 visit(s). AOSLO images will not be taken until the Principal Investigator or qualified designee has reviewed all non-AOSLO inclusion and exclusion criteria carefully. Once the patient is determined to be eligible

to participate based on all non-AOSLO criteria, a montage of AOSLO images will be acquired from the central 5.7 degrees surrounding fixation in each eye. AOSLO images will be analyzed and evaluated for selection of at least 7 ROIs in each eye, located at similar distances from the fovea and with less than 2 standard deviations difference between average cone spacing z-scores between the 2 eyes. The patient will return for a second baseline visit during which AOSLO images will be acquired again, but this time focusing on the ROIs that were identified during baseline visit 1. If the second set of AOSLO images of at least 7 ROIS are suitable for cone spacing and density measures in each eye (as determined by the Principal Investigator), and the patient continues to express interest to participate in the study, then the patient will be randomized. Upon randomization, the patient (now referred to as the “study subject” or “subject”) is considered enrolled into the study and will then be qualified for surgery. The subject will proceed to the Baseline 2 and Baseline 3 visits prior to surgery. The timing for each Baseline visit is as follows:

- Baseline 1 will occur within approximately 7 weeks (21 days) of implant surgery;
- Baseline 2 will occur within approximately 4 weeks of Baseline 1;
- Baseline 3 will occur at the time of medical evaluation for surgery which will occur within \leq 4 days before device surgical implant.

Masking:

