4.1 Summary

The following analysis populations are planned for this study:

- The **screening population**, which is to include all subjects who provide (a) baseline screening (including any demographic, visual acuity, or photographic data), and (b) informed consent.
- The **safety population**, which is to include all patients who receive the investigational intervention.
- The **intent-to-treat efficacy population**, which is to include all patients who are randomized. This is the primary population for the efficacy analyses.
- The **per-protocol efficacy population**, which is to include all patients in the intent-to-treat efficacy population, excluding patients with major protocol deviations.

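### Protocol 4.8 randomises before Baseline 3, where the HIV test, the only baseline pregnancy test and the pre-operative tests are scheduled, so a participant found ineligible there can enter the all-randomised primary analysis without an implant

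*Protocol*

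**What the plan says.** **Order of events.** Protocol 4.8 describes consent, screening, a first AOSLO montage, a second AOSLO visit at the selected regions of interest (ROIs), and randomisation if at least 7 ROIs per eye are suitable. The randomised patient is then enrolled and qualified for surgery. The next sentence reads: "The subject will proceed to the Baseline 2 and Baseline 3 visits prior to surgery".

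**Eligibility review.** The same section says: "AOSLO images will not be taken until the Principal Investigator or qualified designee has reviewed all non-AOSLO inclusion and exclusion criteria carefully".

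**Content of Baseline 3.** Table 1 marks the HIV test, serum chemistry, haematology, urinalysis, the ECG and the urine pregnancy test at Baseline 3 and at no other baseline visit. Its footnote 2 says: "Baseline 3 will occur < 4 days prior to implant surgery". Footnote 3 ties the timing of the ECG and pre-operative laboratory tests to the operating room's requirements.

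**Link to eligibility.** Exclusion 18 says: "A laboratory test for HIV will be performed, and a positive result is also an exclusion criterion". Exclusion 17 covers pregnancy, and inclusion 7 requires fitness for the surgery.

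**Analysis population.** SAP 4.1 defines the intent-to-treat efficacy population as one "which is to include all patients who are randomized" and makes it primary for efficacy. Protocol 6.2 agrees.

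**Missing outcomes.** SAP 7.6.2 imputes follow-up values in steps. The last step covers eyes with no follow-up data, and the analysis that includes it is the primary one.

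**Assignments.** SAP 3.3 builds the list from ten right-eye and ten left-eye assignments.

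**The concern.** A test that can exclude a participant should be read before that participant is randomised. Here the scheduled order is the reverse for at least two explicit exclusions and for clearance for surgery. A participant who then fails is already in the primary population, has had no surgery, and has no post-operative images. Intent-to-treat analysis properly keeps such a person in, which is why the plan should not create such cases when it can avoid them.

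Three things are at stake. A pair of eyes with no implant may dilute the estimated effect. Its contribution to the primary result comes entirely from the imputation model. One of a short list of assignments is also spent on someone who was never going to be treated.

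There is a second, smaller problem. Section 4.8 can be read as placing Baseline 2 either before or after randomisation, and a site cannot settle this from that section alone.

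**Working it through.** **1. Are the results known before randomisation?**

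| Item | Eligibility criterion | Scheduled | Required before randomisation? |
|---|---|---|---|
| HIV test | Exclusion 18 | Baseline 3 | Not stated |
| Urine pregnancy test | Exclusion 17 | Baseline 3 (only baseline test) | Not stated |
| Pre-operative laboratory tests, ECG | Inclusion 7 | Baseline 3 | Not stated |

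Section 4.8 places Baseline 3 after randomisation, at the medical evaluation for surgery. Its rule that every non-AOSLO criterion is reviewed before the first AOSLO image cannot be met on this schedule. The first image is taken at Baseline 1, before these tests are due. The rule and Table 1 conflict.

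**2. Where does Baseline 2 fall?**

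- Before randomisation: 4.8 makes a suitable second AOSLO set a condition of randomisation. Section 4.7 requires ROIs confirmed on two baseline visits before a subject is eligible to enrol. Table 1 footnote 5 makes Baseline 2 the visit that verifies the ROIs. SAP 2.3.1 and 7.5.1.1 say ROIs are fixed before randomisation.
- After randomisation: the one sentence in 4.8 quoted above.

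The weight of the text is on the first order.

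**3. The stated window.** Section 4.8 says: "Baseline 1 will occur within approximately 7 weeks (21 days) of implant surgery". Seven weeks is 7 × 7 = 49 days. Table 1 footnote 1 and SAP 7.5.1.1 both say 7 weeks.

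**4. The plan's own sample size.** Inputs are a difference of 0.084 arcminutes (SAP 3.1.2), SD of the paired difference 0.11 (SAP 3.1.5), two-sided alpha 0.05 (SAP 3.1.1) and 15% loss (SAP 3.1.4).

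- Standardised effect d = 0.084 / 0.11 = 0.764.
- Paired t-test power from the noncentral t with n − 1 degrees of freedom and noncentrality d√n: n = 16 gives 0.814, n = 17 gives 0.840, n = 20 gives 0.899.
- The smallest n for 80% is 16. The SAP states 17, which is close. Allowing for loss, 17 / 0.85 = 20, as stated.

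**5. Illustration of dilution.** Assume k of N randomised participants never receive the implant, have a true mean difference of zero and are still analysed. With f = k/N, the mean difference is 0.084(1 − f). Power is computed in two ways: with the SD held at 0.11, and with the mixture SD √(0.11² + f(1 − f) × 0.084²). For N = 20 and k = 1, the mean is 0.0798 and the mixture SD is √(0.0121 + 0.0475 × 0.007056) = 0.1115.

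| N | k | Mean difference | Power, SD 0.11 | Power, mixture SD |
|---|---|---|---|---|
| 20 | 0 | 0.0840 | 0.899 | 0.899 |
| 20 | 1 | 0.0798 | 0.868 | 0.859 |
| 20 | 2 | 0.0756 | 0.830 | 0.811 |
| 20 | 3 | 0.0714 | 0.786 | 0.757 |
| 17 | 1 | 0.0791 | 0.794 | 0.782 |

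For N = 30, about the number in Protocol section 4, the mixture calculation gives 0.981 with none and 0.972, 0.960, 0.944 and 0.924 with one to four.

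**The case against.** The strongest reply is that this is a matter of wording and that the plan already contains the safeguards.

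- **ROI verification.** A reader might infer that ROIs are verified after the eye is assigned and that the baseline is exposed to knowledge of it. The documents do not support this. Step 2 shows that the rest of the text places verification first. Protocol 4.8 masks the graders and image staff, and SAP 3.3 keeps the backup copies of the list from the PI and study personnel. What stands is a contradiction to reconcile.
- **ERG.** A reader might add inclusion 11e, "reduction of both rod and cone electroretinogram (ERG) responses", to the late tests. Table 1 footnote 4 lets the ERG be done at any point in the 7 weeks before surgery, so it need not come late. I leave it out.
- **One-month window.** Section 4.7 says of evaluations, "which are completed within 1 month of the initial screening visit, can be used to establish eligibility". This is permissive. It does not say that only those evaluations count, so it does not conflict with Baseline 3.
- **Laboratory timing.** Footnote 3 may let the HIV and other tests be done earlier, depending on the operating room. That is fair, but it does not tie them to randomisation.
- **Table layout.** Some Table 1 rows look shifted in the text available. The Baseline 3 reading does not rest on columns alone: footnote 3 treats these as pre-operative tests, and 4.8 describes Baseline 3 as the medical evaluation for surgery.
- **Intent-to-treat.** Keeping ineligible or untreated participants is ordinary practice. SAP 4.2 lists both as major deviations, so they leave the per-protocol set. Each person supplies both eyes, so a late exclusion does not unbalance the arms. All true, but the per-protocol analysis is not primary, and none of this is a reason to randomise before exclusion tests are read.
- **Power figures.** They assume a count of late failures and zero effect in imputed pairs. The SAP does not specify the imputation model, and one that includes treatment need not give a null pair. The calculation is a paired t-test on two-year change in arcminutes, whereas SAP 7.5.1.1 plans a Wilcoxon test on 36-month changes in z-scores. This objection stands, and the figures are illustrative only.

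**Conclusion.** The point holds in a limited form. The schedule lets a patient be randomised and enrolled before the HIV, pregnancy and pre-operative results are known, against 4.8's own rule on prior review. Such a participant can enter the primary analysis untreated, with both eyes' 36-month outcomes imputed. A reader might conclude that ineligible people will enter. The documents show only that they can.

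The size cannot be fixed from the documents. On the stated assumptions, up to three such participants among 20 would cost roughly 3 to 14 percentage points of power (0.90 down to between 0.87 and 0.76). At 30, up to four would cost about 6 points at most (0.981 to 0.924). With no late failures there is no loss.

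The Baseline 2 sentence is an internal contradiction and not evidence of late ROI verification. The 21-day figure is a slip, not evidence that the schedule is infeasible. The section should be corrected because the remedy is cheap and prevents avoidable untreated pairs. Nothing here shows that the primary comparison is biased.

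**What to change.** 1. In Protocol 4.8, make randomisation the last step before surgery: after Baseline 2 has verified at least 7 ROIs per eye and after the Baseline 3 eligibility results are available. Define randomisation as release of that participant's eye assignment to the surgeon, and match SAP 3.3 to this.
2. Correct the sentence that sends randomised subjects to Baseline 2 and Baseline 3, so that both visits precede randomisation.
3. State which results must be known before the first AOSLO image and which before randomisation, so that the review rule agrees with Table 1.
4. Reconcile the 7-week and 21-day figures in 4.8 with Table 1.

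The cost is wording in the protocol and a matching line in the SAP. No test or visit is added, and the list is already generated in advance. The small downside is that the assigned eye is known only in the last days before surgery.

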5.1 Safety Monitoring Committee

The SMC will be convened prior to trial initiation to review the protocol and will review accumulated data during the staggered implantation phase (see section 4.0) and on a regular basis during the trial. The Committee will also meet ad hoc to address any problems of significance related to participant safety brought to its attention. The committee will consider whether a protocol modification is indicated. If changes in the protocol are indicated, recommendations will be made to the sponsor who will act on such recommendations in a timely manner.

5.2 Adverse Experience Reporting

All adverse events, either observed by the Investigator or one of his/her medical collaborators, or reported by the participant spontaneously, or in response to direct questioning, will be reported. Any adverse event regardless of severity or potential association with the test article (considered to be the implant or CNTF) or study procedures must be documented in study records by the Investigator and promptly reported to the sponsor.

5.3 Obligations of Site Investigators

The Principal Investigator is obligated to promptly report to the sponsor any adverse event that may reasonably be regarded as caused by, or probably caused by the test article or study procedures. This protocol additionally requires the Investigator to report all other adverse events regardless of their severity or potential association with the test article or treatment procedures. When reporting an adverse event, the Investigator must assign a severity grade to each event and declare an opinion on the relatedness of the event to the study test article or procedure.

For any serious or unexpected adverse event, the sponsor must be notified *within 24 hours* of when the Investigator first learns of the occurrence of the event. Expedited reporting requirements for serious adverse events are described below (see Section 5.2.1.1). Adequate information must be collected with supporting documentation to complete a standard MedWatch Form FDA 3500A for submission to the sponsor.

For adverse events considered non-serious, expected or routine and where the specific event type is explicitly tracked on study case report forms, timely recording is considered acceptable when the data are reported on the schedule established for regular case report forms in the study Manual of Procedures.

If the participant reaches the final scheduled follow-up visit, any new adverse events, as well as follow-up information for ongoing adverse events, must be recorded. For participants who withdraw prematurely, adverse events should be followed until resolved or 30 days after the final study visit. In any case, serious adverse events that are not resolved or considered to be chronic within 30 days of the final study visit must be followed by the investigator until they become resolved or are considered to be chronic (stabilized for at least 30 days).

5.3.1 Expedited Reporting Responsibilities of the Site

When expedited reporting of a serious adverse event (SAE) is required (or expected to be required) for event types described in Sections 5.2.3.1 or 5.2.3.2, the Investigator (or the Study Coordinator) will promptly:

- Notify the medical monitor and SMC chair of any SAE within 24 hours of the knowledge of the occurrence of the SAE and fax a SAER Form to the medical monitor at [contact].
- Assess and report the causality of the event.
- If applicable, provide the Medical Monitor with immediate follow-up information necessary to make an initial assessment of the event, in order to meet reporting obligations.

- Provide the medical monitor with subsequent follow-up information to finalize the SAE (in the form of a follow-up SAER, answered SAE query form, discharge summary, laboratory reports, etc. as applicable).

